3.2.2 End date of the Observational Period

The end date of the Observational Period will be the date of Visit 3, which is approximately 6 months after Baseline for subjects completing the Treatment Period, or the Withdrawal Visit for subjects who discontinued during the Observational Period. If a subject does not have a Visit 3 for any reason including death, then either the date of early withdrawal or the date of last known dose of study drug during the Observational Period, whichever is later, will define the end date of the Observational Period.

3.3 Definition of Baseline values

Concomitant AEDs at Baseline are defined as AEDs given at the start date of LCM or the date of Visit 1 in case of a missing start date of LCM.

For all other variables, Baseline data are the values collected at Visit 1.

Baseline for the partial-onset seizure frequency per 28 days will be derived from the data of the Historical Seizure Count form as described in Section 3.10.4.

3.4 Protocol deviations

A Per-Protocol Set will not be used for the analyses. However, important protocol deviations will be identified prior to database lock and listed in the Clinical Study Report.

The definition of important protocol deviations is initiated by the Clinical Data Manager with the input from the PRA Project Manager and other stakeholders (please refer to applicable UCB submission excellence program [SEP] standard operating procedures [SOPs] for details). Search criteria for potential protocol deviations will be detailed in the important protocol deviations document, which is an addendum to the Data Cleaning Plan. Where possible, protocol deviations are to be identified programmatically.

Data cleaning meetings will be held where important protocol deviations identified programmatically or in other supplemental documents based on data not collected in the CRF are reviewed and discussed. Data Evaluation Meetings (DEMs) will also be held and during these meetings the protocol deviations will be discussed and any trends identified. Preparation and conduct of the Data Cleaning and Data Evaluation Meetings will be performed as per UCB's current SEP SOPs and Guidelines.

3.5 Analysis sets

For this study, 4 analysis sets are defined:

3.5.1 Enrolled Set

The Enrolled Set (ES) is defined as all patients included in the study and for whom at least Visit 1 is documented. The ES will be used for patient disposition and patient data listings only.

3.5.2 Safety Set

The Safety Set (SS) is defined as all patients included in this study receiving treatment with LCM at least once in the study. The SS will be used for the analysis of the retention and discontinuation rates, time to discontinuation, safety data, and Baseline characteristics of the patients.

3.5.3 Full Analysis Set

The Full Analysis Set (FAS) is defined as all patients in the SS who have at least 1 post-Baseline PGIC or seizure assessment. The FAS will be used for the analysis of the primary and most secondary variables including any subgroup analyses. In addition, demographic and baseline summaries will be based on the FAS.

3.5.4 Modified FAS

The modified FAS is defined as all patients in the FAS ≥ 16 years of age and treated with daily LCM doses ≤ 400 mg, representing the on-label use of LCM. All efficacy analyses excluding subgroup analyses, demographic and baseline summaries and some safety summaries will be repeated in the modified FAS.

On-label use for this study is defined as receiving a LCM daily dose ≤ 400 mg. Patients who receive at least one dose of LCM that is >400 mg will be excluded from the modified FAS.

3.6 Treatment assignment and treatment groups

All patients treated received LCM with the dosage determined at the discretion of the physician. Data summaries will be presented based on the total number of patients and will not be differentiated by LCM dose with the exception of the frequency of seizures occurring at doses of LCM < 200 mg and ADRs presented by dose. Where appropriate, LCM dose will be presented on patient data listings.

3.7 Center pooling strategy

No data pooling strategies will be applied for analyses within this study. Unless otherwise stated, data from all centers will be combined and summarized collectively.

3.8 Coding dictionaries

Medical history and ADRs will be coded using version 16.1 of the Medical Dictionary for Regulatory Activities (MedDRA®). For coding of prior and concomitant medication, version Sep 2013 of World Health Organization Drug Dictionary (WHO DD) will be used.

3.9 Changes to protocol-defined analyses

Not applicable.

3.10 Definitions of study-specific derived variables

3.10.1 Relative Day

The relative day of a visit or an event with respect to the first application of LCM will be presented in patient data listings. Relative days will be calculated as follows:

1. If the start (stop) date occurred prior to the start of LCM, the relative day is calculated as start (stop) date minus date of first LCM intake. That means that in patient data listings, relative days based on this situation will be preceded by a ‘-’.
2. If the start (stop) date occurred on or after the start of LCM, the relative day is calculated as start (stop) date minus date of first LCM intake + 1.

If the visit or event occurred after the date of last dose of LCM, then the relative day is derived using the date of last dose of LCM rather than the date of first LCM intake. In this situation the relative days will be calculated as follows:

- The relative day is calculated as start (stop) date minus last dose date. In patient data listings, relative days based on this situation will be preceded by a ‘+’ to differentiate this situation from item 2 above.

Relative days will not be presented for partial or missing dates.

3.10.2 Age

The age will be given in years and will be calculated as year of informed consent date – year of birth.

3.10.3 Time since first diagnosis

The time since first diagnosis will be given in years and will be derived applying all the rules for missing date imputation (see Section 4.2.3) with the following formula:

$$(\text{Start date of LCM} - \text{date of diagnosis}) / 365.25$$

Only completed years will be considered, ie, decimal places will be ignored. In cases where the start date of LCM is missing, the date of Visit 1 will be used instead.

3.10.4 Seizure Frequency

Partial-onset seizure frequency per 28 days will be derived from the number of days in the considered time interval (D) for which seizure information was provided:

$$(\text{Number of seizures over the specified time interval}) \times (28/D)$$

The considered time interval is defined as 56 days for the historical seizure count at Baseline (8 weeks x 7 days) and as date of actual visit – date of previous visit for all other time points. Note

if any subjects have a diagnosis of epilepsy less than 8 weeks prior to study entry, then site will be instructed to give their best approximation of the 8-week seizure frequency and the reported historical seizure count will be assumed to be representative of the full 8 weeks. The seizure frequency per 28 days cannot be derived using the time from diagnosis of epilepsy to study start as the time period for reporting the historical seizure frequency for such subjects because only the month and year are collected for the date of diagnosis.

The absolute and percentage change in partial-onset seizure frequency from Baseline (Visit 1) will be derived for Visit 2 and Visit 3.

A responder is defined as a patient who experiences a 50% or greater reduction in partial-onset seizure frequency from Visit 1 (Baseline) to Visit 3 (Month 6 or end of Observation Period).

The seizure-free status (Yes/No) at the end of the 6-month Observation Period will be determined for each patient. A patient is seizure-free if the seizure count at Visit 3 (Month 6 or end of the Observation Period) is 0, otherwise the patient is not seizure-free at the end of the 6-month Observation Period.

The frequency of seizures with and without secondary generalization will also be calculated based upon the response to the question 'Number of partial-onset seizures with secondary generalization' in the CRF. If the number with secondary generalization is known, the number of seizures with secondary generalization will be taken from the CRF and the number of seizures without secondary generalization will be calculated as overall number of seizures – number of seizures with secondary generalization.

Partial-onset seizure frequency per 28 days at a dose of <200mg/day at Visit 2 and Visit 3 will be derived from the number of days in the considered time interval (D) for which seizure information was provided where the subject was on a dose of <200mg/day according the dosing log for LCM:

(Number of seizures over the specified time interval) x (28/D).

The number of seizures is the number of partial onset seizures at a dose <200mg/day. The time interval for Visit 2 is the number of days between the Visit 1 and Visit 2 dates where the subject was on a dose <200mg/day for LCM. The time interval for Visit 3 is the number of days between the Visit 2 and Visit 3 dates where the subject was on a dose <200mg/day for LCM. The change from baseline will then be derived by subtracting the partial onset seizure frequency per 28 days reported at Baseline from the partial onset seizure frequency per 28 days on a dose <200mg/day at Visit 2 and Visit 3. If the number at less than 200 mg/day is not applicable, then the number of partial-onset seizures at less than 200 mg/day is treated as missing.

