8 SELECTION AND WITHDRAWAL OF PATIENTS

8.1 Selection criteria

Before any data are collected for any patient in this NIS, written data consent will be properly executed and documented.

The following selection criteria must be followed for patients entering the NIS:

1. Patient has never been treated with LCM prior to this NIS or treatment with LCM for the first time started no earlier than 7 days prior to enrollment in this NIS.
2. The decision by the treating physician to prescribe LCM falls within current standard clinical practice, and the treatment decision is clearly separated from the decision to consider inclusion of the patient in the NIS.
3. A Patient Data Consent form is signed and dated by the patient and/or by the parent(s) or legal representative.
4. Patient is a male or female ≥ 16 years of age.

5. Patient must have a diagnosis of BTRE secondary to low-grade glioma (World Health Organization Grade 1 to 2 at time of enrollment).
6. Patient has a retrospective Baseline seizure frequency of at least 1 partial-onset seizure in the 8 weeks prior to start of LCM treatment.
7. Patient does not have a previous diagnosis of epilepsy before tumor onset.
8. Patient does not have brain metastases.
9. Patient has a Karnofsky performance status scale index $\geq 60\%$.
10. Patient is currently taking only 1 or 2 Baseline AEDs for epilepsy other than LCM.
11. Patient has received a maximum of 4 different lifetime AEDs ever before entering the NIS.

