15 RECOMMENDED SCHEDULE OF STUDY ASSESSMENTS

Table 15–1: Recommended schedule of study assessments

Assessments	Visit 1 ^a (Baseline)	Visit 2 Approximately 3 months after Baseline according to routine practice ^b	Visit 3 (End of Observation Period or Withdrawal Visit ^c) Approximately 6 months after Baseline according to routine practice ^b
Signed data consent	X		
Demographic data	X		
Medical history	X ^d		
Seizure history	X ^d		
Tumor diagnosis and grade (including review of most recent brain imaging results [CT or MRI])	X		X
Prior and concomitant tumor management (surgical procedures, chemotherapies, radiotherapy)	X ^d		X
Prior and concomitant AEDs	X	X	X
Other prior and concomitant epilepsy treatment	X	X	X
Other prior and concomitant relevant medications	X ^d	X	X
Verification of selection criteria	X		
Documentation of LCM administration	X	X	X
Documentation of seizure information (including seizure frequency and type) ^e		X	X
Karnofsky performance status	X	X	X
EQ-5D-5L	X		X

Table 15–1: Recommended schedule of study assessments

Assessments	Visit 1 ^a (Baseline)	Visit 2 Approximately 3 months after Baseline according to routine practice ^b	Visit 3 (End of Observation Period or Withdrawal Visit ^c) Approximately 6 months after Baseline according to routine practice ^b
MDASI-BT	X		X
PGIC			X
CGIC			X
Recording of ADRs and AESIs	X	X	X
Withdrawal criteria		X	X

ADR=adverse drug reactions; AED=antiepileptic drug; AESI=adverse event of special interest; CGIC=Clinical Global Impression of Change; CT=computerized tomography; EQ-5D-5L=5-Level EuroQol-5 Dimension Quality of Life Assessment; LCM=lacosamide; MRI=magnetic resonance imaging; MDASI-BT=M.D. Anderson Symptom Inventory - Brain Tumor; PGIC=Patient Global Impression of Change

^a Visit 1 will be performed after the decision is taken to start adjunctive LCM therapy. Treatment with LCM should be initiated according to routine clinical practice. If the first dose of LCM is given on the same day as Visit 1, it should be administered after Baseline assessments are complete. Previous treatment with LCM is allowed for up to 7 days prior to enrollment.

^b The frequency of visits after Visit 1 will be based on local clinical practice and the patients' requirements. The clinical procedures performed at each visit will also follow local clinical practice. It is estimated that patients will be followed at least every 3 months.

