^c Patients who discontinue early should perform Visit 3 assessments as a Withdrawal Visit.

^d During the previous 8 weeks and relevant information in the past according to the physician's decision.

^e The treating physician will evaluate at each visit, as part of standard practice with the patient, the frequency and type of seizures experienced by the patient since the previous study visit.

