2.3 Study design and conduct

EP0045 is a multicenter, prospective, single-arm non-interventional study (NIS) conducted at specialized sites utilizing LCM added to existing treatment with 1 or 2 AEDs in patients ≥ 16 years of age with BTRE secondary to low-grade tumor.

There are expected to be approximately 100 patients enrolled in the study (see Section 2.4) with 93 evaluable patients expected. Approximately 20 specialized centers are planned for participation. The expected recruitment period is 12 months. The Observation Period per patient will be up to 6 months after initiation of LCM treatment.

The patients will be followed as per current clinical practice for their condition. No additional diagnostic or monitoring procedures will be applied. The choices of AED treatment are made independently by the treating physician in the regular course of practice and are, therefore, independent of participation in this NIS.

The clinical evaluation of patients with BTRE secondary to low-grade tumor will be performed by the treating physician following routine clinical practice. All visits and assessments will be scheduled and conducted per routine clinical practice. It is anticipated that visits will occur every 3 months based on standard of care; therefore, each patient will have approximately 3 visits during their participation in this study. These visits will consist of:

- Visit 1, Baseline
- Visit 2, approximately 3 months after Baseline according to routine practice
- Visit 3, approximately 6 months after Baseline according to routine practice or end of Observation Period

Patients who discontinue early should perform Visit 3 assessments as a Withdrawal Visit.

At the Baseline Visit patient demographics, seizure frequency, and Baseline epilepsy medication will be documented. Assessment of Baseline seizure frequency will be assessed by retrospectively collecting seizure incidence during a period of 8 weeks prior to first LCM intake.

During the study seizure counts will be collected at each visit. At the last visit the patient's impression of change using the PGIC score will be recorded. The management and reporting of ADRs and AESIs will be handled according to international drug safety regulations and UCB procedures.

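### The first post-Baseline seizure interval opens at Visit 1, not at first lacosamide dose, so Visit 2 seizure frequencies are distorted for patients who did not start on the day of Visit 1

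*SAP*

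**What the plan says.** **Baseline window.** SAP 2.3 describes Baseline as "retrospectively collecting seizure incidence during a period of 8 weeks prior to first LCM intake". Protocol 8.1, criterion 6, uses the same endpoint: "at least 1 partial-onset seizure in the 8 weeks prior to start of LCM treatment". SAP 3.10.4 fixes the length: "The considered time interval is defined as 56 days for the historical seizure count at Baseline (8 weeks x 7 days".

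**Follow-up intervals.** The same SAP sentence sets D, the days in the interval, as the actual visit date minus "date of previous visit for all other time points". For the first follow-up visit the previous visit is Visit 1. Collection matches this: footnote e of Protocol Table 15-1 has the physician evaluate "the frequency and type of seizures experienced by the patient since the previous study visit".

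**When LCM starts.** Footnote a of the same table says "Visit 1 will be performed after the decision is taken to start adjunctive LCM therapy" and adds "Previous treatment with LCM is allowed for up to 7 days prior to enrollment". It also provides for a first dose on the day of Visit 1. No maximum delay after Visit 1 is stated.

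**Low-dose analysis.** For the frequency below 200 mg/day, SAP 3.10.4 says "The time interval for Visit 2 is the number of days between the Visit 1 and Visit 2 dates", restricted by the dosing log to days below that dose.

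**Other variables.** The safety Observational Period (SAP 3.2.1), time to discontinuation (3.10.7) and exposure (3.10.14) all start at LCM start.

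**The concern.** Baseline is anchored on first dose and follow-up on Visit 1. They meet only when LCM starts on the day of Visit 1, and no SAP rule re-anchors the overall seizure frequency in the other cases.

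- **LCM starts after Visit 1.** The days before the first dose sit in the numerator and denominator of a rate that is read as on-treatment.
- **LCM started before Visit 1.** The treated days up to Visit 1 lie after Baseline and before the first follow-up interval, so their seizures enter no frequency.

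At stake are the Visit 2 frequency and its absolute and percentage change. Where Visit 2 is absent, the primary responder variable and the secondary seizure-free variable are also at stake.

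The protocol's amendment log suggests how this arose: criterion 6 was moved from Visit 1 to LCM start and prior LCM was allowed, but no matching change to the follow-up anchor is listed.

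**Working it through.** **The plan's own figure.** The plan gives no number for the gap between Visit 1 and first dose. Its one quantitative target reproduces: 1.96² × 0.6 × 0.4 / 0.10² = 92.2, so 93 evaluable patients, with half-width 1.96 × √(0.24/93) = 0.0996. This point does not change it.

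**Late start, Visit 2.** Inputs: D runs from Visit 1 (SAP 3.10.4); scheduled Visit 2 is at 90 days (SAP 3.2.1); delay d is assumed. Let p be the true reduction and f = d/D. If the seizure rate stays at Baseline until first dose and is constant afterwards, the observed rate relative to Baseline is f + (1 − f)(1 − p), so:

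observed reduction = p(1 − f)

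With p = 50% and D = 90:

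| Assumed delay | Untreated share f | Observed reduction |
|---|---|---|
| 3 days | 3.3% | 48.3% |
| 7 days | 7.8% | 46.1% |
| 14 days | 15.6% | 42.2% |
| 28 days | 31.1% | 34.4% |

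Counted from first dose, each row returns 50%.

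**Late start, small counts.** Criterion 6 admits patients with 1 seizure in 8 weeks: 1 × 28/56 = 0.5 per 28 days. Suppose the only seizure in a 90-day first interval comes before the first dose. The SAP rule gives 28/90 = 0.311, a reduction of 1 − 0.311/0.5 = 37.8%. From first dose there are no seizures, a 100% reduction.

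**Early start.** Seven treated days before Visit 1, followed by 90 days, leave 7/97 = 7.2% of treated days outside every frequency interval. With a constant rate the frequency is unbiased and only data are lost. If the early days differ, it shifts. Example: Baseline 2 in 56 days (1.0 per 28 days), first dose 7 days before Visit 1, one seizure in those 7 days and one in the next 83.

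- SAP rule: 1 × 28/83 = 0.34, a 66% reduction.
- From first dose: 2 × 28/90 = 0.62, a 38% reduction.

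**Below 200 mg/day.** D counts only dosing-log days below that dose, so untreated days after Visit 1 drop out. Low-dose days before Visit 1 are still lost, because the interval opens at Visit 1.

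**Reach into the Visit 3 variables.** With a Visit 2 on file, the Visit 3 interval runs from Visit 2 and contains none of the days in question. Without one it runs from Visit 1, and the true reduction needed to score as a responder is 0.5/(1 − f). SAP 3.2.1 assigns visits after day 135 to Visit 3:

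| First follow-up visit | 7-day delay | 14-day delay |
|---|---|---|
| Day 136 | 52.7% | 55.7% |
| Day 180 | 52.0% | 54.2% |

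Seizure-free status is more fragile, since it requires a count of 0. One pre-dose seizure removes it. The same seizure against a Baseline count of 1 leaves a responder at day 180: 28/180 = 0.156, a reduction of 1 − 0.156/0.5 = 69%.

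**The case against.** The strongest reply is that the mismatch rarely reaches the primary result. Most of that stands, and it rules out several stronger readings.

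- **That the responder rate is generally biased.** A reader might infer this, but a Visit 3 interval that follows a recorded Visit 2 is untouched.
- **That every Visit 2 frequency is wrong.** Footnote a expressly foresees a first dose on the day of Visit 1, and those patients carry no error. The share of other patients is not given.
- **That responders face thresholds of 54% to 65%.** The formula gives 54.2% (7-day delay, day 90), 59.2% (14-day, day 90) and 65.2% (14-day, day 60). By the numeric windows in SAP 3.2.1, however, visits up to day 135 are Visit 2 and yield no responder status. These figures apply only if an early withdrawal visit counts as Visit 3 despite that window. The parenthesis in SAP 3.2.1 and Protocol section 5 point that way, but the SAP does not say which rule prevails.
- **That pre-dose days are counted twice, in Baseline and in follow-up.** SAP 2.3 and 3.3 take Baseline from a historical count documented at Visit 1, and a retrospective count taken then cannot include later days. The definition is loose, but double counting is not established.
- **That treated days before Visit 1 are lost altogether.** They are lost only to seizure frequency. They count in exposure, time to discontinuation and the safety period.

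It is also fair that a late start understates benefit, that an early-start gap is capped at 7 days, and that the study is descriptive. None of this removes the defect: followed exactly, the SAP puts untreated days into a rate presented as on-treatment.

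**Conclusion.** The point holds for the Visit 2 frequency and change in patients whose LCM start differs from Visit 1. For late starters a true reduction p reads as p(1 − f): 46.1% instead of 50% for a 7-day delay in a 90-day interval. For early starters up to 7 treated days are omitted, also from the low-dose analysis, with bias only if those days differ from later ones and in no fixed direction.

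The primary responder and secondary seizure-free variables are affected only where no Visit 2 precedes the Visit 3 value, and then modestly for response: a required true reduction of 52.0% or 54.2% at day 180.

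These sizes rest on constant seizure rates before and after first dose and on assumed delays. The documents give neither the distribution of the gap nor the number of patients without a Visit 2. The point merits correction but does not call the usual primary calculation into question.

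**What to change.** **If counts can still be defined.** In footnote e of Table 15-1 and in SAP 3.10.4, start both the seizure count and D for the first post-Baseline visit at the first LCM dose. Use the same start for the days below 200 mg/day. Do not change D alone: the count would still run from Visit 1, and numerator and denominator would cover different days. Same-day starters keep their present values.

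**If counts were already taken from Visit 1.** Keep the visit anchor and state it as a limitation. Tabulate the gap between Visit 1 and LCM start, and repeat the Visit 2 change, responder and seizure-free summaries without patients whose gap exceeds a number of days fixed in advance.

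**Cost.** One footnote and a short SAP edit, using visit and dosing dates already collected. The first route needs some re-querying of first follow-up counts, with the recall problems that brings. The second costs a slightly smaller sensitivity set.

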5 STUDY DESIGN

EP0045 is a multicenter, prospective, single-arm NIS conducted at specialized sites utilizing LCM added to existing treatment with 1 or 2 Baseline AEDs in patients ≥ 16 years of age with BTRE secondary to low-grade tumor. There are expected to be approximately 100 patients enrolled in the study (see Section 11.5).

The patients will be followed as per current clinical practice for their condition. No additional diagnostic or monitoring procedures will be applied. The choices of AED treatment are made independently by the treating physician in the regular course of practice and are, therefore, independent of participation in this NIS.

The observation of the first patient will start after a positive opinion to conduct the study has been received by the responsible ethics committee(s) (Section 12.4.2) and the regulatory authority(ies) if applicable (Section 12.4.3).

Eligible patients will be enrolled consecutively and all patients (and/or their parents or legal representatives) have to accept in writing that his/her medical data will be used for the evaluation of the study results by signing a study-specific Patient Data Consent form according to local requirements.

The clinical evaluation of patients with BTRE secondary to low-grade tumor will be performed by the treating physician following routine clinical practice. All visits and assessments will be scheduled and conducted per routine clinical practice. It is anticipated that visits will occur every 3 months based on standard of care; therefore, each patient will have approximately 3 visits during their participation in this study. These visits will consist of:

- Visit 1, Baseline
- Visit 2, approximately 3 months after Baseline according to routine practice
- Visit 3, approximately 6 months after Baseline according to routine practice or end of Observation Period

Patients who discontinue early should perform Visit 3 assessments as a Withdrawal Visit.

All data to be collected at Visits 1, 2, and 3 are described in Section 15, Table 15-1 (to be collected as available). The management and reporting of ADRs and AESIs will be handled according to international drug safety regulations and UCB procedures.

Documentation of all study assessments is to be performed by the treating physician in the study-specific electronic Documentation form (eDF). Although the study is noninterventional in nature, every attempt must be made to assess all participating patients in the same way.

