8.2 Withdrawal criteria

Patients are free to withdraw from the study at any time, without prejudice to their continued care.

Physicians are free to add or withdraw any medication or to withdraw the patient from the study at their own discretion.

If a patient needs to increase the dose of the Baseline AEDs (1 or 2) or needs to be treated with more than 2 AEDs other than LCM, these changes can be implemented, but the patient will be withdrawn from the study.

If the physician elects to stop LCM treatment, the patient will be withdrawn from the study.

The primary reason for withdrawal must be documented in the patient's eDF. When the primary reason for withdrawal is an ADR, the ADR must be reported as described in Section [10.1.7](#).

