11.5 Determination of sample size

A sample size of 100 enrolled patients to obtain 93 evaluable patients was chosen for this study based on an expected 6-month responder rate (where a responder is a patient experiencing a 50% or greater reduction in partial onset seizure frequency from Visit 1 [Baseline] to Visit 3 [Month 6

or end of Observation Period]) of 60% with an expected precision in the 95% CI of approximately $\pm 10\%$ for this estimate of response.

When the sample size is 93, a 2-sided 95% CI for a single proportion using the large sample normal approximation will extend 0.10 from the observed proportion for an expected proportion of 0.60.

Recruitment will be stopped at 100 enrolled patients and withdrawals will not be replaced.

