4 STATISTICAL/ANALYTICAL ISSUES

No formal statistical analyses will be performed. All variables will be summarized using descriptive statistics; there will be no inferential analyses. For continuous variables, summary statistics (number of available observations, mean, standard deviation, minimum, lower quartile, median, upper quartile and maximum) will be tabulated. Categorical variables will be summarized by the number of patients and the percent of patients in each category. For time to event variables, medians derived using Kaplan-Meier estimates and corresponding 95% CIs will be presented. Supporting Kaplan-Meier plots will be presented.

Data from patients who prematurely withdraw from the study will be analyzed up to the final visit attended.

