8.1.1 Derivations of primary efficacy variables

8.1.1.1 Seizure frequency response

A responder is defined as a patient who experiences a 50% or greater reduction in partial-onset seizure frequency from Visit 1 (Baseline) to Visit 3 (Month 6 or end of Observation Period).

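### The primary responder rule does not require LCM to be ongoing, and the Visit 3 seizure interval does not stop at the last LCM dose, so a patient who stopped LCM can count as a responder on partly or mostly off-LCM time

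*SAP*

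**What the plan says.** The relevant rules are spread over both documents.

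- **Stopping LCM ends participation.** Protocol 8.2: "If the physician elects to stop LCM treatment, the patient will be withdrawn from the study".
- **The last visit supplies the Visit 3 data.** Protocol 5 and Table 15-1, footnote c: "Patients who discontinue early should perform Visit 3 assessments as a Withdrawal Visit".
- **Visit timing is not fixed.** Protocol 5: "All visits and assessments will be scheduled and conducted per routine clinical practice". Visits are expected about every 3 months. Footnote b of Table 15-1 lets frequency follow local practice and the patient's needs, and estimates follow-up at least that often.
- **The seizure count runs visit to visit.** Under footnote e of Table 15-1 the physician records all seizures since the last study visit. SAP 3.10.4 sets the matching interval as the actual visit date minus the "date of previous visit for all other time points".
- **Data after stopping are used.** SAP 4: "Data from patients who prematurely withdraw from the study will be analyzed up to the final visit attended". SAP 3.2.2 ends the Observational Period of a discontinuing patient at the Withdrawal Visit, not at the last dose.
- **Response depends on frequency alone.** SAP 8.1.1.1: "A responder is defined as a patient who experiences a 50% or greater reduction in partial-onset seizure frequency" from Visit 1 to Visit 3. Protocol 4.1 and 11.3.1 and SAP 3.10.4 and 8.1.2.1 say the same. Seizure-free status (SAP 3.10.4) needs only a zero count at Visit 3.
- **Two other derivations do follow exposure.** Time to discontinuation (SAP 3.10.7) ends at the last LCM administration. The seizure rate below 200 mg/day (SAP 3.10.4) uses only the days that the dosing log shows at that dose.

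**The concern.** The primary objective is the effectiveness of LCM added to 1 or 2 AEDs, and the responder rate is one of its two primary variables. If the seizure count behind a response was gathered largely after LCM was stopped, and perhaps after other AED treatment was changed, it says little about LCM. A reader of the final table could not tell such responders from those who were still taking the drug. The same applies to seizure-free status, and to a PGIC rating given some time after the last dose. There is no comparator arm against which the effect could be noticed, and the SAP does not say whether follow-up regardless of LCM use is intended.

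**Working it through.** **1. The plan's own figure.** Protocol 11.5 states: "When the sample size is 93, a 2-sided 95% CI for a single proportion" by the normal approximation "will extend 0.10 from the observed proportion for an expected proportion of 0.60".

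n = 1.96² × 0.60 × 0.40 / 0.10² = 92.2, rounded up to 93. The half-width at n = 93 is 1.96 × √(0.24/93) = 0.0996. The figure reproduces, and this point does not change it.

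**2. Share of the Visit 3 interval that is off LCM.** With days counted from Visit 1 and a last dose on or after Visit 2:

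off-LCM share = (Visit 3 day − last-dose day) / (Visit 3 day − Visit 2 day)

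The nominal visit days are 90 and 180 (SAP 3.2.1). The last-dose days are assumptions, because the documents give none.

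| Visit 2 | Last dose | Visit 3 | Off-LCM days / interval | Share |
|---|---|---|---|---|
| 90 | 100 | 180 | 80/90 | 89% |
| 90 | 120 | 180 | 60/90 | 67% |
| 90 | 135 | 180 | 45/90 | 50% |
| 90 | 150 | 180 | 30/90 | 33% |
| 90 | 166 | 180 | 14/90 | 16% |
| 90 | 180 | 180 | 0/90 | 0% |
| 90 | 95 | 136 | 41/46 | 89% |
| missed | 95 | 180 | 85/180 | 47% |

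When Visit 2 is missed, the interval starts at Visit 1. The interval is mostly off LCM only when the last dose falls in its first half.

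**3. The rule applied to the first row.** Assume a Baseline of 2 seizures in 56 days: 2 × 28/56 = 1.0 per 28 days. With 1 seizure in the 90 days, the frequency is 1 × 28/90 = 0.31. The reduction is 69%, so the patient is a responder although 80 of the 90 days were off LCM.

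The rule can also go the other way. Response requires a frequency of at most 0.5, that is a count of at most 0.5 × 90/28 = 1.6, so at most 1 seizure. Two seizures in the 80 off-LCM days give 2 × 28/90 = 0.62, a 38% reduction. That is a non-response even if no seizure occurred on LCM.

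**4. Effect on the rate.** One patient is 1/93 = 1.08 percentage points. Assume 56 of 93 patients respond (60.2%; Clopper-Pearson 49.5 to 70.2), and that k of the 56 had stopped LCM before the visit. If those k are scored as non-responders on the same denominator:

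| k (assumed) | Rate | 95% CI |
|---|---|---|
| 1 | 59.1% | 48.5 to 69.2 |
| 3 | 57.0% | 46.3 to 67.2 |
| 5 | 54.8% | 44.2 to 65.2 |

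The documents give no k. Because rescoring only removes successes, the as-observed rate can equal or exceed the rescored one and cannot fall below it.

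**5. Which Withdrawal Visits reach the responder rate.** SAP 3.2.1 assigns visits up to day 135 to Visit 2 and later ones to Visit 3, yet the same line names the Withdrawal Visit as Visit 3. Read literally, a Withdrawal Visit at day 135 or earlier is Visit 2. That patient then has no Visit 3 value and drops out of the available-data denominator of SAP 8.1.2.1. Read the other way, the patient stays in. The day-180 example is Visit 3 on both readings.

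**The case against.** The strongest reply is that the Withdrawal Visit may be the occasion on which LCM is stopped, which makes the off-LCM share zero. Footnote b of Table 15-1 allows earlier visits, and a patient with an adverse reaction may well be seen soon. This stands as a limit on how often the problem arises. It does not remove it: no section ties the visit to the last dose, and SAP 3.10.1 has a rule for visits after the last dose.

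A second reply is that using the final assessment of withdrawn patients is a legitimate choice, and that the protocol defines response at Month 6 or the end of the Observation Period. That is also fair. Scoring every stopper as a non-responder makes a composite of response and retention, and would fail a patient seen one day after the last dose. It therefore belongs beside the protocol-defined rate and should not replace it.

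Third, retention and discontinuations by reason are reported, visits after the last dose can be identified in the listings, and all analyses are descriptive. So no test or sample size is affected. But these tables do not show how many responders had stopped LCM.

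Several stronger readings are tempting and are not supported:

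- *That the rate is inflated by a stated total.* The number of stoppers, the gap from last dose to visit, and the share meeting the 50% rule are all absent. Nor is every stopper who meets the rule a false responder: some will have responded on LCM and stopped late.
- *That the bias favours LCM.* Relative to the true on-LCM effect the direction is unknown, because seizures may rise after stopping.
- *That being both a responder and a discontinuation is a contradiction.* Response and tolerability are separate variables.
- *That withdrawal for a Baseline AED dose increase can be picked out from the termination reason.* The SAP quotes only adverse drug reaction and lack of efficacy as coded reasons.

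**Conclusion.** The gap is real. Under the current text a patient who stopped LCM can be counted as a responder or as seizure-free on an interval that is partly off LCM, and mostly so when the last dose falls in the first half of the interval. The size per patient is about 1.1 points at n = 93. The total cannot be derived from the documents.

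The only direction that can be stated is arithmetical: on the same denominator, the as-observed rate is at least as high as the rate that scores stoppers as non-responders. The conclusion assumes no unseen document, such as CRF completion instructions, fixes the Withdrawal Visit at the last dose. It concerns how the responder percentage is read. The planned precision is unaffected.

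**What to change.** 1. In SAP 8.1.2.1 and 8.2.6, keep the as-observed rates. Add, in the FAS, a responder rate and a seizure-free rate with Clopper-Pearson intervals. A patient counts as a success only if the existing rule is met and the dosing log shows LCM ongoing at the date of the Visit 3 or Withdrawal Visit.
2. Score patients who stopped LCM before that visit as non-responders (and not seizure-free) and keep them in the denominator, including those whose Withdrawal Visit was at day 135 or earlier. State how a last dose on the visit day is classified.
3. Show PGIC at Visit 3 split by LCM ongoing yes/no.
4. Reconcile the day-135 window in SAP 3.2.1 with its statement that the Withdrawal Visit is Visit 3, so that both sets of rates use the same visit.

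The dosing log, the last-administration date (SAP 3.10.14) and the LCM-ongoing status (SAP 10.1) are already planned, so the cost is SAP wording and one extra table. Cutting the count itself at the last dose is not proposed, because the documents do not show seizure dates or counts split at that point being collected. The downside is that the added rates will be equal to or lower than the as-observed ones.
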